2.18 Ethics and Regulatory Issues

The pilot version of this trial protocol has been approved by Health Canada and a waiver of IND was granted by the FDA. Current regulatory applications are underway in several countries in Europe. All participating institutions will obtain local ethics approval and we will obtain informed consent from patients or their surrogates before starting study procedures. Telephone or e-consent strategies, where allowed by local ethics boards will be acceptable. We justify the use of a placebo as trial participants will receive increased monitoring and follow up, which may translate into improved outcomes. At 6 months, we will be making contact with the patient or their alternative contact. If we detect patients are ‘in need’ of further clinical interventions, local research personnel making the contact will be trained by local investigators to direct the patient back to the referring clinical service or other local service as appropriate.

As this trial was already underway before January 20, 2020 and has already been approved by local IRBs at more than half of the US sites already, using a single IRB is not a cost-effective strategy to activate the remaining US sites. This is consistent with the policy on single IRB exception determinations.⁹⁰

2.19 Confidentiality

Information about study participants will be kept confidential and will be managed in accordance with the following rules:

- All study-related information will be stored securely.
- All study-participant information will be stored in locked file cabinets, or locked room, as applicable, and accessible only to study personnel.
- All paper and eCRFs will be identified only by a coded participant number.
- ***All databases will be password protected and secured within electronic data capture systems (EDCS).***

If a participant revokes authorization to collect or use personal health information, the clinical site retains the ability to use all information collected prior to the revocation of participant authorization unless otherwise specified. Records pertaining to the clinical trial will be retained and maintained for a period of 15 years in compliance with Health Canada requirements.

2.20 Serious Adverse Events and Safety Reporting

In the context of an acute critical illness, all patients eligible for the VICToRY Trial are at risk of adverse events (AEs). Following Canadian guidelines for AE reporting in academic critical care trials, expected AEs were pre-specified as trial outcomes and will not be reported as AEs. These events will be recorded in the electronic data capture system as part of data collection. No other AEs will be reported.

Patients will be monitored daily for SAEs. Clinical sites will document all unexpected SAEs in the EDCS. The local principal investigator, with support from the trial principal investigators and Coordinating Centre, will determine if the SAE is possibly related to the study intervention (see Appendix D for SAE and causality/relatedness definitions). The trial principal investigators and Coordinating Centre will also support the local principal investigator with

determining if the SAE is unexpected. Unexpected SAEs must be reported to the Coordinating Centre via the EDCS within 24 hours of the local principal investigator becoming aware of the unexpected SAE. Unexpected SAEs that are considered to be possibly related to the trial intervention will be reported to all applicable regulatory authorities and participating site principal investigators by the Coordinating Centre in an expedited manner. Clinical sites are also responsible for reporting SAEs to the Institutional Review Board (IRB)/Research Ethics Board (REB) of record as per their IRB/REB of record's reporting requirements.

In accordance with Health Canada requirements for reporting suspected unexpected serious adverse reactions (SUSARS), the Coordinating Centre will inform all applicable regulatory agencies of any unexpected SAEs that are possibly related to the trial intervention within 15 days (if it is neither fatal nor life threatening), or within 7 days after becoming aware of the information (if it is fatal or life threatening). AEs and SAEs that are expected, but not serious, will not be reported to regulatory agencies, but rather monitored and tracked by the Coordinating Centre. The Coordinating Centre will report to applicable regulatory agencies "expected" SAEs, where an increase in the rate of occurrence or severity, was judged to be clinically important.

All CERU staff will be supervised by [name] and along with Drs. [name] and [name], and will form the Executive Committee which will be responsible for the day-to-day management of the trial. They will be responsible for all aspects of coordinating this trial including training, data management, quality assurance and monitoring, and analysis. The team at the CERU will be supported by the Steering Committee that will provide specific scientific and operational input. We have also constituted a Stakeholder Committee, comprised of the Steering Committee and additional site investigators, research coordinators and patient advisors, to obtain input from a broader group of stakeholders.

Appendices

- Appendix A: Results of Most Recent Meta-analysis of Intravenous Vitamin C
- Appendix B: Schedule of Assessments
- Appendix C: Interim Analysis and Sample Size Considerations
- Appendix D: SAE and causality/relatedness definitions
- Appendix E: References

[figure not shown]
Appendix A: Results of Most Recent Meta-analysis of Intravenous Vitamin C⁴⁹

Fig. 2 Overall mortality. A Random-effect meta-analysis, and B sensitivity analysis with fixed-effect meta-analysis

Appendix B: Schedule of Assessments

SCHEDULE OF ASSESSMENTS	Screening / Baseline Day 1	Day 2	Day 3	Day 4	Day 5	Day 6	Day 7	Day 8	Ad Hoc	Outcomes (d/c to 90 days max)	6 Month Follow-Up	Early withdrawal
SCREENING/Pre-RANDOMIZATION (collected once)												
Obtain Consent												
Rule-out Pregnancy (if applicable) as SOC												
Inclusion Criteria met (age; burn size)												
Exclusion Criteria - none present												
BASELINE (collected once at beginning of study period)												
Randomization												
Demographics, Comorbidities, APACHE II Score, hospital & ACU admit date/time												
Burn Injury Assessment (date/time; type; % TBSA)												
Clinical Frailty Scale assessment												
TRAUMA (collected once at baseline)												
Traumatic Brain Injury, GCS, other trauma												
SOFA (record from ACU admission to 3 days after last dose of IP)												
PaO ₂ /FiO ₂ (lowest)												
Platelets (lowest)												
MAP (lowest)												
MICROBIOLOGY (record from >72 hours after ACU admission to ACU discharge for a maximum of 3 months)												
Gram negative bacteremias												
VENTILATION/RRT (record data from hospital admission to hospital discharge for a maximum of 3 months)												
Invasive Mechanical Ventilation												
Renal Replacement Therapy (dialysis)												
VASOPRESSORS and INOTROPES (record from ACU admission to ACU discharge for a maximum of 3 months)												
Vasopressors/Inotropes (highest hourly rate) for each: dobutamine, dopamine, epinephrine, levosimendan, milrinone, norepinephrine, phenylephrine, vasopressin.												
VITAMIN C DOSING (record all doses received)												

SCHEDULE OF ASSESSMENTS	Screening / Baseline Day 1	Day 2	Day 3	Day 4	Day 5	Day 6	Day 7	Day 8	Ad Hoc	Outcomes (d/c to 90 days max)	6 Month Follow-Up	Early withdrawal
Vitamin C administration (start/stop times; volume infused; interruptions)												
DAILY LABORATORY (record labs ordered as SOC from ACU admission to 3 days after last dose of IP)												
Creatinine, serum (highest)												
Bilirubin, Total (highest)												
Urea (highest)												
Glucose (closest to 8:00 A.M.)												
Hypoglycemic events (record up to 3/day)												
Lactate Dehydrogenase (LDH) (highest)												
pH, arterial (lowest)												
HCO ₃ (bicarbonate), serum (lowest)												
Albumin (lowest)												
Hemoglobin (lowest)												
Haptoglobin (highest)												
Reticulocyte count (highest)												
Clinical suspicion of hemolysis? (yes/no)												
FLUID BALANCE (record from ACU admission to 3 days after last dose of IP)												
Were blood products given? (yes/no)												
Packed RBCs (volume)												
Plasma (volume)												
Albumin, 5%, 20%, 25%, other (volume)												
Urine output (mL)												
Total fluid volume IN (mL)												
Total fluid volume OUT (mL)												
BURN RELATED PROCEDURES (record from hospital admission to hospital discharge for a maximum of 3 months)												
Date, planned or unplanned, location of procedure, and type of procedure												
PROTOCOL VIOLATIONS (record from randomization to 3 days after last dose of IP)												
Type of violation, SI awareness, action taken												
EVENTS OF INTEREST (record related events that result in stopping IP early, from start of IP to stop of IP)												
New diagnosis of oxalate kidney stone												
Severe hemolysis												
Severe acid-base imbalance												

SCHEDULE OF ASSESSMENTS	Screening / Baseline Day 1	Day 2	Day 3	Day 4	Day 5	Day 6	Day 7	Day 8	Ad Hoc	Outcomes (d/c to 90 days max)	6 Month Follow-Up	Early withdrawal
Severe electrolyte imbalance												
Refractory hypoglycemia												
SERIOUS ADVERSE EVENTS (recorded within 24 hrs of awareness, from randomization to 3 days after the last dose of IP)												
Event description, seriousness, outcome, expectedness, relationship to IP, action taken with IP, action taken to treat event												
HOSPITAL OVERVIEW (recorded once after hospital discharge to a maximum of 3 months)												
ACU – date of discharge, death, or consent withdrawal.												
Hospital – date of discharge, death, or consent withdrawal.												
Location discharged to or cause of death.												
COVID-19 (collected once and recorded at hospital discharge, or 3 months after admission)												
COVID-19 Status, negative, positive, presumed positive, not tested/unknown and date of result or determination												
SURVIVAL ASSESSMENT (collected once at 6 months after admission (+/- 14 days))												
Alive or deceased, date, source of data.												
If data not obtained, record efforts made, and date last known to be alive.												
HEALTH RELATED QUALITY OF LIFE ASSESSMENTS (collected once at 6 months after admission (+/- 14 days))												
SF-36 questionnaire												
Katz ADL questionnaire												
Lawton IADL questionnaire												
Data Query Resolution (resolve after data entry milestones: hospital overview and survival/6-month assessments)												
Data query checks are built into the EDCS and will generate queries to address missing, inconsistent, and illogical data.												

Data Quality Management and Source Verification/Monitoring

- The study management team will review recruitment reports monthly to identify and address slow enrollment and areas of concern.
- Monitoring visits to conduct source verification and confirm compliance with the protocol and regulatory processes will be conducted throughout the course of the study.
- A Touch Base webinar to debrief will be scheduled after enrollment of the first 2 subjects.
- An initial monitoring visit, either onsite or remote, will be conducted after data entry through hospital discharge has been completed for at least 2 enrolled patients.
- Ongoing monitoring and visits will be risk based and determined by the Executive Committee after review of the findings of the initial monitoring visit.

Glossary of Terms

ACU Acute Care Unit

ADL Activities of Daily Living

EDCS Electronic Data Capture System

GCS Glasgow Coma Scale

IADL Instrumental Activities of Daily Living

IP Investigational Product

mL millilitre, milliliter, millilitres, milliliters

% percentage

SF Short Form

SI Site Investigator

SOC Standard of Care

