The safety profile for vitamin C in ICU patients is remarkably favourable.⁶⁷ Real-time in the field monitoring of safety events has not revealed any safety issues (personal communication, McGuff Pharmaceuticals, Inc., Department of Regulatory Affairs, Ascor® (Ascorbic Acid Injection, USP) PADER Synopsis, Year 5, NDA 209112). However, there are several complications that may develop which will be closely monitored as ‘Events of Interest’ or outcomes in this trial. One of the potential risks is the formation of calcium oxalate crystals in renal tubule. However, this occurs at much higher doses than those being tested in the VICToRY Trial. Cancer patients, for example, sometimes receive vitamin C doses approximately 40-50 times greater than the dose we are planning to administer albeit over a longer period of time.^{68,69} We will nonetheless monitor acute kidney injury (as an outcome in this trial).

Another potential risk, albeit rare, is factitious hyperglycemia as recorded by capillary blood sugar point-of-care devices as the molecular structure of vitamin C and glucose are similar. This phenomenon does not occur with core lab assays and some point-of-care devices.^{70,71} Accordingly, we are going to mandate that glucose can only be measured with one of the 3 following systems up to 7 days after the last dose of the investigational product (even if patient is transferred on ward) : 1) core lab, 2) point-of-care arterial blood gas machine that has been validated in the setting of high plasma concentrations of vitamin C, 3) Nova Biomedical StatStrip glucometer that has been validated to be accurate in the presence of high concentrations of ascorbic acid. Episodes of true hypoglycemia (<3.8 mmol/L) will be captured in the case report form.

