- 3) We have a Data Monitoring Committee which is charged with the responsibility for ensuring the integrity of the trial. They have and will continue to review all serious adverse events (SAE) and will have the right to trigger an ad hoc safety review if 2 or more similar SAEs are observed that cause concern. In addition, by group (but still blinded) they have and will continue to review events of interest, rates of kidney injury (KDIGO classification of acute kidney injury) and use of renal replacement therapy on an annual basis. In addition, they will review the results of planned interim analyses and provide recommendations regarding the ongoing safety of the VICToRY trial. Two formal interim analysis will be performed to assess increased POD+death in the vitamin C arm after one-third and two-thirds of the patients are enrolled (see section 2.16).

In summary, recent studies provide us with a strong signal that high-dose intravenous vitamin C may be beneficial in septic patients. While the pre-clinical data related to burns are compelling, the clinical data in burn patients are too sparse to convince clinicians of the therapeutic benefits. We aim to conduct a large scale, multi-center trial of intravenous vitamin C in burns to establish the efficacy of our proposed intervention.

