2.7 What is the proposed duration of follow-up?

Patient clinical status will be monitored daily during the acute care unit stay for up to 3 days after termination of study IP (maximum 7 days). Hospital outcomes will be abstracted from the chart once the patient is discharged.

2.8 and 2.9 What are the proposed primary and secondary outcome measures?

The primary outcome for this phase III trial is persistent organ dysfunction (POD)+death at 28 days, a novel composite endpoint that combines being alive and being free of organ support (inotropes or vasopressors or mechanical circulatory assistance, renal replacement therapy and mechanical ventilation).⁷⁷

The most important secondary endpoint of this trial will be “time to discharge alive from hospital.” The other secondary outcomes will be the components of 28-day POD which include mortality, use of inotropes or vasopressors or mechanical circulatory assistance, renal replacement therapy and mechanical ventilation and POD-free days in the first 28 days.

Tertiary outcomes will include intensive care unit (ICU) outcomes (e.g. length of stay, duration of mechanical ventilation, and readmission rates); hospital outcomes (hospital mortality, length of stay, bacteremia with gram-negative bacilli, and readmission rates); and 6-month outcomes (mortality, health related quality of life and physical function domain of the Short Form-36 (SF-36) questionnaire, activities of daily living and instrumental activities of daily living). We will also record frequency of operative procedures for burn care, presence of inhalation injury, blood transfusions, and other major cost drivers to support our economic evaluation.

2.10 What is the proposed sample size and what is the justification for the assumptions underlying the power calculation?

The primary outcome for this trial is PODS+death at 28 days after randomization. Based on estimates from currently available pooled data from the RE-ENERGIZE study with $\geq 20\%$ TBSA (n=539), we estimate that the 28-day PODS rate will be 27%. Based on our simulations accounting for two interim analyses (see Tables in Appendix C), we estimate that with 333 subjects per arm, we would achieve 78% power to observe a reduction at a one-sided alpha of 0.025 (or two-sided alpha=0.05) if the rate of PODS at 28 days was reduced from 27% to 18% (RRR=33.3%).

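### Appendix B counts an event of interest only if it is judged related, stops the drug and occurs during dosing, so harms are under-counted; acute kidney injury is called an outcome but is neither listed nor analysed

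*Combined protocol and SAP*

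**What the plan says.** Section 1.5 says there are "several complications that may develop which will be closely monitored as" events of interest or as outcomes. It attaches no condition about cause, stopping of the drug or timing. On the kidney it adds: "We will nonetheless monitor acute kidney injury (as an outcome in this trial". It also has the Data Monitoring Committee (DMC) review, by group but still blinded, the events of interest and "rates of kidney injury (KDIGO classification of acute kidney injury) and use of renal replacement therapy on an annual basis".

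Appendix B sets the recording rule: "EVENTS OF INTEREST (record related events that result in stopping IP early, from start of IP to stop of IP". The rows beneath it are new oxalate kidney stone, severe hemolysis, severe acid-base imbalance, severe electrolyte imbalance and refractory hypoglycemia.

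Sections 2.8/2.9 give the outcome lists. After time to discharge alive, "The other secondary outcomes will be the components of 28-day POD which include mortality" and the organ supports, including renal replacement therapy (RRT), plus POD-free days. "Tertiary outcomes will include intensive care unit (ICU) outcomes", hospital outcomes and 6-month outcomes. AKI is in none of these lists, and neither is any of the five events of interest.

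Section 2.20 says "expected AEs were pre-specified as trial outcomes and will not be reported as AEs", that no other adverse events will be reported, and that sites document unexpected serious adverse events (SAEs).

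**The concern.** The recording rule has three conditions that must all hold: the event is judged related, it leads to early stopping, and it falls between the start and stop of the drug. The first two are judgements about the event rather than facts about whether it happened. Appendix D's wording for a possibly related SAE requires that other conditions do not reasonably explain the event. Section 1.5 itself describes metabolic acidosis as reported in single cases where several factors coincide, so such an event could easily fail that test.

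Safety is half of the stated objective in section 1.1, and section 1.4 intends treatment of all thermally injured patients if the trial is positive. A count that is low because of how it was collected could be read, by the DMC or in the final report, as a low rate of harm.

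For the kidney the problem is different. Section 1.3 cites a renal-failure odds ratio of 5.4 (CI 1.1 to 26, p = 0.06) in a retrospective burn study, and more RRT in one randomized trial of continuous infusion. Both used regimens other than the one tested here. The plan responds by naming AKI as an outcome, then gives it no place in the outcome lists or the analysis.

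**Working it through.** The plan states no figure on this point. The check is to compare its parts, and then to illustrate size under assumed rates.

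**1. Who can contribute an event.** An event must have stopped the drug early, so a patient who receives all 16 doses contributes none. Sections 2.13/2.14 expect compliance above 90%. That figure is not the share of patients who complete dosing, but it suggests that most patients are excluded by the rule.

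**2. What else is recorded.** Appendix B, both arms, without the three conditions:

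| Harm | Record outside the events-of-interest form |
|---|---|
| Hemolysis | LDH, hemoglobin, haptoglobin, reticulocytes, daily yes/no for suspected hemolysis |
| Acid-base | Lowest arterial pH, lowest bicarbonate |
| Hypoglycemia | Daily glucose, up to 3 hypoglycemic events per day |
| Electrolytes | None dedicated: no sodium, potassium or calcium in the daily labs |
| Oxalate stone | None dedicated |
| AKI (not on the form) | Creatinine, urea, urine output; RRT to hospital discharge, maximum 3 months |

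Except for RRT, these run to 3 days after the last dose. Laboratory values are recorded only if ordered as standard of care.

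**3. The SAE route.** The SAE window also runs to 3 days after the last dose, but section 2.20 tells sites to document unexpected SAEs. Harms already named in section 1.5 could be classed as expected. Section 2.20 says that expected events are covered as trial outcomes, yet sections 2.8/2.9 list none of the five.

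**4. AKI.** Section 2.16 analyses binary secondary outcomes like the primary, so RRT, as a POD component, gets an adjusted relative risk. AKI short of RRT has no definition, baseline rule, window or analysis. A baseline rule matters because section 2.5 admits patients with existing kidney injury or failure.

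**5. Size, by illustration.** The documents give neither the rates of these events nor the share that would pass the filter, so both are assumed. Let a share *f* of events be captured, equal in both arms. The expected relative risk is (*f*·p₁)/(*f*·p₀) = p₁/p₀, so it is unchanged. The risk difference becomes *f*·(p₁ − p₀), and power falls.

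Power uses the two-proportion normal approximation, n = 333 per arm, two-sided 5%:

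power = Φ{[√n·|p₁ − p₀| − 1.96·√(2·p̄·(1 − p̄))] / √(p₀(1 − p₀) + p₁(1 − p₁))}

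As a check, 27% versus 18% gives 79.6%, against the plan's 78% after two interim looks.

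- 5% versus 10%, full capture: (18.248·0.05 − 1.96·0.3725)/0.3708 = 0.49, so 69%. Expected events are 333·0.05 = 16.7 and 333·0.10 = 33.3.
- One-quarter capture, 1.25% versus 2.5%: (18.248·0.0125 − 1.96·0.1918)/0.1916 = −0.77, so 22%. Expected events are 4.2 and 8.3.

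| Control risk (true RR 2.0) | *f* = 1 | *f* = 0.5 | *f* = 0.25 | *f* = 0.1 |
|---|---|---|---|---|
| 2% | 33% | 18% | 11% | 7% |
| 5% | 69% | 40% | 22% | 11% |
| 10% | 95% | 69% | 40% | 18% |

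The approximation is rough where counts are small. In the 2% row at *f* = 0.1 only 0.7 control events are expected.

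**The case against.** The five rows match the reasons named in section 1.5 for discontinuing study product, so the form can be read as a log of why the drug was stopped, within a data strategy that section 2.4 calls minimal. That is a fair account of its purpose. But the DMC is also to review events of interest by group, and for that use the restriction matters.

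Three stronger readings are tempting, and the documents do not support them.

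- *No unbiased comparison of the drug's harms is possible.* Most of the feared harms have unfiltered records in both arms. Site staff other than pharmacy are blinded, so the filter should act alike in each arm. Bias would need relatedness or stopping decisions to differ by arm, and nothing shows that they do.
- *The DMC sees a filtered kidney count.* AKI is not on the events-of-interest form. The DMC reviews KDIGO rates and RRT separately, by group.
- *The window always closes at about four days.* Treatment is nominally 96 hours, but missed doses can be made up within 24 hours and the dosing row has boxes to Day 7. A Day 6 event may fall inside it.

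A stone or electrolyte disturbance could also reach the SAE form, which has an expectedness field. That helps only if the event is serious and the site documents it despite the limit to unexpected SAEs in section 2.20.

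**Conclusion.** The concern holds in a limited form. The rule under-counts the five events of interest, and for new oxalate stones and severe electrolyte imbalance there is no other dedicated record. For hemolysis, acid-base disturbance and hypoglycemia the loss is smaller, because daily data allow a comparison by arm, subject to the standard-of-care limit on labs. The consequence is reduced sensitivity and a table that could be misread as reassurance.

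The loss cannot be fixed from the documents. Under the assumed range it runs from modest to severe. For rare events even full capture leaves low power (33% at a 2% control risk), so the gain is honest counts and intervals rather than a decisive test.

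The AKI point is one of reconciliation. The data are mostly collected and the DMC reviews them, but sections 1.5, 2.8/2.9 and 2.16 do not agree on whether AKI is an outcome, and only RRT has a planned final analysis.

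**What to change.** 1. Reword the Appendix B row so that all five events are recorded in both arms, whatever the judged cause and whether or not the drug was stopped, from first dose to at least 3 days after the last dose (the existing SAE and lab window). Record new oxalate stones to hospital discharge. Keep relatedness and action taken as fields on the form. This changes what is recorded, not when the drug is stopped.
2. Report counts by arm for all recorded events, and for the related, drug-stopping subset. For patients enrolled under the current rule, abstract the events from the chart where possible, or show them separately.
3. List KDIGO AKI as a safety outcome in sections 2.8/2.9, derived from the creatinine, urine output and RRT data already collected. State the baseline rule and window, and report it by arm as a relative risk with 95% CI. Say that AKI without RRT is not captured beyond 3 days after the last dose.
4. Reconcile sections 1.5, 2.8/2.9 and 2.20 with Appendix B, so that every event treated as a trial outcome appears in the outcome list.

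The cost is a wording change, a few more form entries per site, some chart review for earlier patients and one more table. No new patient tests are needed.

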Given the 30-36% relative risk reduction in mortality observed in the meta-analysis reported in section 1.2, we believe this treatment effect to be plausible. The simulated power under various effect sizes accounting for the interim analyses is provided in Appendix C. Based on our several prior studies in this field, we expect to obtain the 28-day PODS status on virtually all patients. Since the randomization is stratified by site and the analysis will control for site, the possible presence of between-site heterogeneity in overall rates will not decrease the power, assuming that the effect of treatment is consistent across sites.

A sample size of 666 patients also provides adequate power for one of our key secondary outcomes, time to discharge from hospital alive. Based on estimates from currently available pooled data from the RE-ENERGIZE study with $\geq 20\%$ TBSA (n=539), we estimate that the median time to hospital discharge is 47 days, by which time no more than 10% would have died. We consider death a competing risk precluding live hospital discharge and, for this outcome, conservatively assume that the intervention has no effect on mortality. With 333 patients per arm followed for up to 182 days and allowing for 5% loss to follow-up, we would achieve 90% power at a two-sided alpha of 0.05 to compare the cumulative incidence of time to alive hospital discharge over 6 months, if the subdistribution hazard ratio of time to live discharge was 1.32. Assuming time to discharge follows an exponential distribution except allowing for the competing risk of death, this effect size would equate to 60% vs. 50% of patients being

discharged alive by day 47 in the intervention and control arm respectively. However, power will decrease due to the interim analysis. The interim analysis will reduce the power by 1% if the RR for PODS+death is 0.667 and the power for time to discharge alive will remain above 80% if the RR of PODS+death is less than 0.85.

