Based on our substantial prior experience with this population, we expect minimal missing data for all 28-day outcomes. However, details of missing data will be provided, and for the primary outcome, we will perform a sensitivity analysis using a graphical pattern-mixture tipping-point approach demonstrating the treatment effect over the possible range of missing outcomes.^{84,85} Lengths of ICU and hospital stay will be reported by arm using the subdistribution cumulative incidence function (CIF), where death is treated as a competing risk precluding the possibility of discharge. The between-arm difference in time to live discharge will be summarized by the subdistribution hazard ratio with 95% confidence intervals and p-values estimated by the Wald test from the Cox proportional hazards model, with site as a random frailty to account for potential between-site heterogeneity and adjusting for the same baseline covariates as for the primary outcome. For this analysis, survivors will be censored at the earliest of last date known alive or 183 days after randomization. Patients who die prior to discharge will be censored after the end of the follow-up period (i.e. >183 days) to account for the competing risk of death. This will yield virtually the same results as the Fine and Gray approach treating death as a competing risk precluding discharge, except we will have incorporated ICU as a random effect. This outcome is also known as time-to-discharge-alive (TTDA). The distribution of ventilator-free days and PODS-free days up to day 28 will be compared between arms by the

empirical distribution function depicting the proportion of people (y-axis) with at least 1 through 28 free days (x-axis) by arm.

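### Hospital discharge dates are scheduled only to 3 months, but time to discharge alive is powered and analysed over six; if the cap is applied, power is about 85–87%, not 90%

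*Combined protocol and SAP*

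**What the plan says.** Sections 2.8 and 2.9 name time to discharge alive from hospital as the leading secondary endpoint.

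- **Power (section 2.10).** "With 333 patients per arm followed for up to 182 days and allowing for 5% loss to follow-up, we would achieve 90% power", two-sided at 0.05, "if the subdistribution hazard ratio of time to live discharge was 1.32". The comparison is of cumulative incidence over 6 months.
- **Analysis (section 2.16).** For this endpoint, "survivors will be censored at the earliest of last date known alive or 183 days after randomization". Patients who die before discharge are censored beyond day 183, so that death acts as a competing risk.
- **Collection (Appendix B).** Hospital and ACU dates of discharge or death sit under "HOSPITAL OVERVIEW (recorded once after hospital discharge to a maximum of 3 months", in a column whose heading also limits it to 90 days. The 6-month rows list alive or deceased, date and source, the date last known alive if contact fails, and the questionnaires. None asks for a discharge date.
- **Follow-up (section 2.7).** Hospital outcomes are taken from the chart after discharge. No upper limit is given.

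**The concern.** The power statement and the censoring rule both need discharges observed to about day 182, and the collection schedule stops at about day 90. The cap does not look like a slip. The same 3-month limit appears for ventilation and renal replacement, vasopressors, microbiology and burn procedures, and the COVID-19 row closes at discharge or 3 months after admission.

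Applied as written, this has three effects.

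1. Discharges between day 90 and day 183 are not recorded, so fewer events support the test than the power calculation assumes.
2. A patient discharged on day 110 and known alive at 6 months is carried to day 183 as never discharged, which flattens the incidence curve after day 90.
3. A patient discharged on day 110 who dies on day 150 cannot be told apart from an in-hospital death, although section 2.16 relies on that distinction. Hospital mortality and length of stay have the same gap after day 90.

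**Working it through.** **Inputs (section 2.10 unless stated).** 333 per arm; 5% loss; two-sided alpha 0.05; subdistribution hazard ratio (SHR) 1.32; 1:1 allocation (section 2.3). For controls, "we estimate that the median time to hospital discharge is 47 days, by which time no more than 10% would have died". The effect is also expressed as "this effect size would equate to 60% vs. 50% of patients being" discharged alive by day 47. Time to discharge is taken as exponential apart from competing deaths. Three months is taken as 90 days.

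**1. Effect size.** ln(0.4)/ln(0.5) = 1.322, which agrees with 1.32.

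**2. Events needed.** Schoenfeld: 4 × (1.960 + 1.282)² / (ln 1.32)² gives about 545 (546 rounded up). Freedman gives 553. For 80% power, Schoenfeld gives 408.

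**3. Main model.** Constant cause-specific hazards, with 50% of controls discharged and 10% dead by day 47.

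- Total hazard L = −ln(0.4)/47 = 0.0195 per day.
- Control incidence C(t) = (0.5/0.6) × (1 − exp(−L·t)).
- Treated incidence = 1 − (1 − C(t))^1.32.
- Events = 333 × 0.95 × (control + treated incidence).
- Power = Φ(√events × ln(1.32)/2 − 1.960).

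*Day 182, reproducing the plan's figure:* C = 0.809; treated 0.888; events = 316.35 × 1.697 = 537; power 89.6%. The stated 90% is reproduced.

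*Day 90:* C = 0.689; treated 0.786; events = 316.35 × 1.475 = 467; power 85.1%.

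**4. Other shapes consistent with section 2.10, all with 5% loss.** The plateau rows take an exponential among those who are ever discharged, with the stated share dying in hospital.

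| Model | Day 182: control / treated | Events | Power | Day 90: control / treated | Events | Power |
|---|---|---|---|---|---|---|
| Cause-specific, 10% dead by day 47 | 0.809 / 0.888 | 537 | 89.6% | 0.689 / 0.786 | 467 | 85.1% |
| Cause-specific, 5% dead by day 47 | 0.868 / 0.931 | 569 | 91.2% | 0.712 / 0.807 | 480 | 86.1% |
| Plateau, 10% | 0.861 / 0.926 | 565 | 91.0% | 0.710 / 0.804 | 479 | 85.9% |
| Plateau, 5% | 0.897 / 0.950 | 585 | 91.9% | 0.723 / 0.816 | 487 | 86.5% |
| Exponential, no room for deaths | 0.932 / 0.971 | 602 | 92.6% | 0.735 / 0.827 | 494 | 87.0% |

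The last row is only an upper bound for power, because it ignores the competing deaths that section 2.10 allows for. Taking 91 or 92 days instead of 90 changes power by at most 0.3 points.

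**5. Simulation.** 4,000 replicates of the subdistribution log-rank test under the main model gave 91.1% power at 182 days and 86.2% at 90 days. The average SHR was 1.32 or 1.33 at both horizons.

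**6. Size of the gap.** In the main model (537 − 467)/537 = 13% of expected live discharges fall after day 90. Under the section 2.16 rule the control curve stays at 0.69 instead of reaching 0.81, and the treated curve at 0.79 instead of 0.89. With 5% dead by day 47, the control figures are 0.71 and 0.87.

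**7. Hazard ratio.** If no event is recorded after day 90, the Cox partial likelihood uses risk sets only up to day 90. Censoring an undischarged patient at day 90 or day 183 gives the same estimate, interval and p-value.

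**The case against.** The strongest reply is that section 2.7 has no cap, so sites may record late discharges anyway, and that the Appendix B wording is loose. This stands in part: the documents conflict, and they do not clearly rule out later dates. It does not settle the matter. The column heading and the COVID-19 row both point to a cut-off at 3 months, and two instructions that differ invite uneven capture between centres. Step 7 also assumes that the cap is applied uniformly.

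The second reply is that little is lost. Power falls by about 4–6 points and stays above 80%. The median of 47 days and most discharges come before day 90. The primary endpoint is at day 28, and section 2.16 gives secondary outcomes a mostly supportive and exploratory role. All of this stands, and it limits the weight of the point.

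A reader might go further in three ways that the documents do not support.

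- **That the 90% figure was miscalculated.** It is correct for 182 days.
- **That the treatment comparison is biased.** Under proportional hazards it is not.
- **That the six-month curve is bound to be wrong, with a true control incidence as high as 93%.** The curve is sound to day 90. After that it is too low only if late inpatients are carried forward as undischarged; if they are censored at day 90 it simply stops. The 93% is 1 − 0.5^(182/47), which is hard to square with up to 10% of patients dead by day 47.

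**Conclusion.** The concern holds as an inconsistency between Appendix B and sections 2.7, 2.10 and 2.16 that should be fixed. It does not threaten the trial's main conclusion. If the 3-month cap is applied, power for time to discharge alive at SHR 1.32 is about 85–87%, and 85.1–86.5% in the models that allow for deaths. The six-month incidence could not be reported correctly: the control arm would read about 0.69–0.71 against about 0.81–0.87, and late post-discharge deaths could not be separated from in-hospital deaths.

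These figures rest on extrapolating the exponential assumption beyond day 47 with 5–10% dead by then. The plateau models would put the control figures slightly higher, at up to 0.72 and 0.90. The further 1-point loss that section 2.10 attributes to the interim analyses at a relative risk of 0.667 is not included.

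**What to change.** Preferred: for patients still in hospital at 3 months, add the dates of hospital and ACU discharge, or of in-hospital death, to the 6-month form, and amend Appendix B to match. The 183-day analysis and the 90% figure can then stand. The cost is one or two fields on a form already completed, plus an edit to the schedule.

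Otherwise: define the endpoint as time to discharge alive by day 90, censor survivors at day 90, drop the six-month incidence, and restate power as about 85%. The section 2.10 statements on how the interim analyses affect this power should be recomputed on the same horizon. This costs only wording and about 5 points of stated power.

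Whichever is chosen, align section 2.7 with it and settle the choice before unblinding, so that the horizon is not picked with the results in view.
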